5. INVESTIGATIONAL PLAN

5.1 PURPOSE

The purpose of this clinical investigation is to demonstrate the safety and effectiveness of the CarboClear Pedicle Screw System ("CarboClear System"), for skeletally mature DDD patients undergoing one level spinal fusion, in combination with interbody fusion device, and requiring immediate, rigid, posterior spinal stabilization of the lumbar and/or sacral spine.

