5.2 STUDY DESIGN

A prospective, multi-center, confirmatory, single arm, study.

A total of up to 55 subjects with DDD at one level from L2 to S1, who have failed to improve with conservative treatment for at least six months prior to enrollment, will participate in this study. At least 30 patients will be enrolled at US sites with the rest being enrolled in sites outside the US.

All patients will be implanted with the investigational device and an FDA cleared PEEK interbody fusion device (Medtronic's Capstone PEEK Spinal System (K073291, K103731, and more); or Medtronic's Crescent PEEK Spinal System (K094025, K133216, and more)), using PLIF or TLIF approach, and undergo interbody spinal fusion. According to the physician discretion, posterolateral spinal fusion may also be performed, using autogenic bone graft (from local and/or iliac crest bone) and/or allogenic bone graft comprised of cancellous and/or corticocancellous bone graft. As Medtronic's Capstone and Crescent Systems are cleared only with autogenous bone graft, only autogenous bone graft will be packed into the cage. In case posterolateral fusion is also conducted, either autogenous bone graft or allogenic bone graft, as detailed above, may be used at this location.

Pre-clinical data (bench testing), as described in the Investigator Brochure, demonstrated equivalency to cleared, rigid, metal, pedicle screw systems with similar intended use, both in terms of test results values and tests failure modes. In addition, clinical data regarding the use of the subject device, which is currently available from an on-going, out-of-the-US (OUS), multi-center study, and is summarized in the Investigator Brochure, also supports the effective and safe use of the investigational device. The discussed confirmatory clinical study is designed to further support the safety and effectiveness of the CarboClear System.

The results of the suggested study will be evaluated in relation to historical-based data, derived from the literature and described in **Section 5.2.1**.

Comparison to retrospective data from the literature regarding metal pedicle screw systems used in conjunction with interbody fusion device will be made in terms of efficacy and safety.

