Individual patient success (*i.e.*, overall success) is defined as a composite endpoint. A patient will be considered a "success" if all primary effectiveness and safety outcome measures listed above are met. As detailed later in this document, the statistical analyses of the suggested study will be descriptive in nature.

During the clinical investigation, the patients will be evaluated preoperatively (baseline), intraoperatively, at discharge, and postoperatively at 6 weeks, 3 months, 6 months, 12 months and 24 months, and then annually, until the last patient completed 2-year follow-up. Radiographic endpoints will be evaluated by two independent reviewers at an imaging core laboratory (Medical Metrics, Inc., Texas). In the case of a disagreement between the two radiographic assessors, a third independent reviewer will evaluate the radiographic images to adjudicate the findings. In addition, a CT scan will be acquired for subjects in which bridging bone status could not be determined form X-Rays, at each time point starting at 6 months post-operatively.

At each evaluation time point, as applicable, the primary and secondary endpoints shall be evaluated (*e.g.*, pain and function evaluations based on patient questionnaires shall be performed pre-operatively and starting at 6-week follow-up visit; fusion assessment will be made starting at 6-month). Complications and adverse events will be evaluated at each follow-up visits and over the course of the clinical trial. Detailed evaluation schedule is provided in **Table 8**.

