The following search terms were utilized: "fusion" [Title/Abstract], OR "arthrodesis" [Title/Abstract], OR "Interbody" [Title/Abstract], OR "Posterolateral" [Title/Abstract]; AND "lumbar" [Title/Abstract], OR "lumbosacral" [Title/Abstract]; AND "degenerative disc disease" [Title/Abstract], OR "disc degeneration" [Title/Abstract], OR "DDD" [Title/Abstract], OR "spondylosis" [Title/Abstract], OR "back pain" [Title/Abstract]. The searches were limited to articles published in "English" [Language], "Humans" [Medical Subject Headings], NOT "case report" [Title], NOT "cadaver" [Title] OR "anatomical" [Title], NOT "children" [Title] OR "adolescent" [Title], NOT kinematic [Title/Abstract] OR "finite element" [Title/Abstract], from April 1997 to 2015. A total of 3,990 reports were obtained.

Eleven eligible studies were selected for the analysis, according to the following criteria:

- (1) subjects were skeletally matured and had undergone spinal fusion for the lumbar and/or sacral spine;
- (2) the intervention included instrumented fusion (interbody and/or posterolateral fusion), in at least one arm of the study;

¹⁹ http://www.ncbi.nlm.nih.gov/pubmed

- (3) indications were DDD with or without degenerative spondylolisthesis (up to Grade I);
- (4) the study reported at least fusion definition and results of fusion rate;
- (5) patients were followed up to at least one year after surgery;
- (6) number of patients was at least 20;
- (7) manuscripts were given priority if published in high ranking journals and quoted in meta-analysis.
- (8) high level of evidence manuscripts (I and II levels).

The flowing manuscripts were selected:

- Fritzell P, Ha¨gg O, Wessberg P, Nordwall A, and the Swedish Lumbar Spine Study Group. Chronic Low Back Pain and Fusion: A Comparison of Three Surgical Techniques. A Prospective Multicenter Randomized Study from the Swedish Lumbar Spine Study Group. *Spine* 2002;27(11):1131–1141.

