Fritzell 2002 (Arm I)	N ₂₄ =43 *	N ₂₄ =21 *	ALIF or PLIF + PLF + PSS	DDD	N ₂₄ =65*	47.3 ± 10.9	-	38.5 ± 18.9	8.8	(19%)
Fritzell 2002 (Arm II)	N ₂₄ =35⁴	N ₂₄ =27 •	PSF + PSS	DDD	N ₂₄ =59*	48.4 ± 11.6	-	33.6 ± 17.9	14.8	(30%)
Zigler 2007	N ₂₄ =71	-	ALIF + PLF + PSS	DDD	N ₂₄ =71	62.7 ± 10.3	40.7	39.8 ± 24.3	22.9	(37%)
Hackenberg 2005	No level st	ratification	TLIF + PLF + PSS	DDD	N ₃₆ =30	58.4 ± 18.4	37.5 ± 19.3	37.0 ± 24.8	21.4	(37%)
Delamarter 2009	-	N ₂₄ =61	ALIF + PLF + PSS	DDD	N ₂₄ =61	64.8 ± 9.5	41.1 ± 23.0	38.7 ± 24.1	26.1	(40%)
Brox 2003	No level st	ratification	PLF + PSS	DDD	N ₁₂ =35	42.0 ± 11.0	26.4 ± 16.4	-	15.6	(37%)

Table 4: Literature Control - Oswestrey Disability Index (ODI) Outcome

* The ODI evaluation was conducted for 65 patients, however the stratification to one and two-level was given to 64 patients that were radiographically evaluated.
* The ODI evaluation was conducted for 59 patients, however the stratification to one and two-level was given to 62 patients that were radiographically evaluated.

	Points Range	Number of Manuscripts	Number of Patients	Weighted Average
12m Δ Improvement (single level)	22.0	1	71	22.0
24m Δ Improvement (single level)	22.9	1	71	22.9
12m Δ Improvement (double level)	23.7	1	61	23.7
24m Δ Improvement (double level)	26.1	1	61	26.1
$12m \Delta Improvement (1 \& 2 levels)$	20.9 – 23.7	4	197	23.4
24m Δ Improvement (1 & 2 levels)	8.8 - 26.1	4 (total of 5 study arms)	286	18.5

Table 5: Literature Control - ODI Reference Results

As can be seen, the similar values were reported for one- and 2-level and for one- and two years, justifying the pooling of the results.

Number of Manuscripts	Number of Patients	Weighted Average Improvement (Δ)	Weighted Average Improvement (%)	Ra	nge
5 (a total of 6 study arms)	321	18.22	32.63%	8.8 (19%)	26.1 (40%)

In addition, the recently published systematic literature review (Phillips *et al.*) mentioned above analyzed published literature to evaluate the efficacy of lumbar arthrodesis for DDD patients, reported "*As a whole, these 12 studies including 1420 fusion patients showed a weighted average improvement in ODI function of* $24.7 \pm 6.2/100$ (47.2% change; 95% CI, 41.3–53.1)" [*emphasis added*]. This correlates with the values listed in the tables.

C. VAS Pain

The following table summarizes the VAS (pain) results, as described in the articles referenced above.

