Single Cohort VAS VAS VAS % Improvement Double **Improvement** (Δ) Procedure Diagnosis Level Level Size 24 m (VASI_{bl}-VAS_{last f.u.}) $(\Delta VAS/VAS_{bl})$ Baseline 12 m Fritzell ALIF or PLIF N₂₄=43* N₂₄=21* DDD N₂₄=65* 65.6 ± 15.2 45.7 ± 26.7 19.9 (30%)-2002 (Arm I) + PLF + PSSFritzell 2002 (Arm N₂₄=35* N₂₄=27 * PSF + PSSDDD N₂₄=59 * 63.3 ± 13.3 40.4 ± 23.9 22.9 (36%) -II) ALIF + PLFZigler N₂₄=71 DDD N₂₄=71 75 ± 14.6 42 ± 28 43 ± 31.6 (43%) 32 -+ PSS 2007 TLIF + PLF Hackenberg No level $N_{36}=30$ 83 ± 26 45 ± 23 48 ± 28 35 DDD (42%)2005 stratification + PSS Delamarter ALIF + PLF 40.3 ± 27.9 38.4 ± 29.8 DDD N₂₄=61 74.7 ± 13.6 36.3 (49%) $N_{24}=61$ -2009 + PSS No level Brox PLF + PSS 39.4 ± 25.5 DDD N₁₂=35 62.1 ± 14.5 22.7 (37%) _ stratification 2003

* The ODI evaluation was conducted for 65 patients, however the stratification to one and two-level was given to 64 patients that were radiographically evaluated.

• The ODI evaluation was conducted for 59 patients, however the stratification to one and two-level was given to 62 patients that were radiographically evaluated.

	Point Range	Number of Manuscripts	Number of Patients	Weighted Average
12m Δ Improvement (single level)	33	1	71	33
24m Δ Improvement (single level)	32	1	71	32
12m Δ Improvement (double level)	34.4	1	61	34.4
24m Δ Improvement (double level)	36.3	1	61	36.3
$12m \Delta Improvement (1 \& 2 levels)$	22.7 - 38	4	197	32.4
$\begin{array}{c} 24m \ \Delta \ Improvement \\ (1 \ \& \ 2 \ levels \) \end{array}$	19.9 - 36.3	4 (total of 5 study arms)	286	28.6

Table 7: Literature Control - VAS Reference Results

As can be seen, the overall patient population had a VAS improvement of around 30 points. In addition, similar values were reported for one- and 2-level and for one- and two years, justifying the pooling of the results.

Number of Manuscripts	Number of Patients	Weighted Average Improvement (Δ)	Weighted Average Improvement (%)	Ra	inge
5 (a total of 6 study arms)	321	27.96	39.47%	19.9 (30%)	36.3 (49%)

In addition, Phillips *et al.* published recently systematic literature review, which analyzed published literature to evaluate the efficacy of lumbar arthrodesis for DDD patients, and reported that "*As a whole, these 12 studies including 1420 fusion patients showed a weighted average improvement in back pain of 36.5 \pm 17.2/100 points (43.3% change; 95% CI, 31.5–55.1)."*

D. Adverse Events

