5.13 STATISTICAL ANALYSIS

5.13.1 SAMPLE SIZE JUSTIFICATION

Fifty five (55) patients will participate in the IDE study. However, the statistical analysis will be conducted for a total sample size of 100 patients as the Company is adding data from ongoing OUS sites to data collected according to this IDE. FDA confirmed that the proposed IDE sample size, in addition to the ongoing OUS data, would be sufficient. It is emphasized, that prospectively enrolled patients at OUS sites will participate in the study presented in this IDE (i.e., will be part of the 55 patients of the IDE study), and will follow the same protocol that representing homogenous cohort of DDD patients with up to Grade I spondylolisthesis and no greater than mild stenosis. Only currently enrolled patients in the ongoing OUS sites that are adequately per IDE protocol (about 45 patients) will be considered in the statistical analysis. Adequacy for OUS study patients being included in the statistical analysis will be based, mainly, on patient meeting the eligibility criteria (inclusion/exclusion) for the IDE study, *i.e.*, DDD patients, with up to Grade I spondylolisthesis and/or with up to mild stenosis (the ongoing OUS study was approved for more heterogenic population). Other parameters, as detailed below, are very similar when comparing the ongoing OUS study and the study suggested in this IDE: The same system and surgical technique are used in both studies. The IDE study includes the use of an interbody fusion device while the OUS study does not. Thus, the data from the OUS study may be regarded as worst case in terms of fusion rates as only posterolateral fusion was made and interbody fusion device was not used. Patient population is

CARBOCLEAR PEDICLE SCREW SYSTEM

considered similar in both studies (demographically, as well as indications wise, as non-DDD patients will not be included in the statistics for the IDE study). The endpoints for the IDE study are also evaluated in the ongoing OUS study, using the same assessment tools: fusion (radiographs), safety, pain (VAS), function (ODI), and patient well-being (SF-12). Follow-up time points are similar in the ongoing OUS study (4 weeks, 3 months, 6 months, 12 months and 24 months) and the suggested IDE study (6 weeks, 3 months, 6 months, 12 months, and 24 months, and then annually, until the last patient completed 2-year follow-up).

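### The pooled primary analysis mixes 55 IDE patients with an interbody cage and about 45 OUS-study patients without one, and no named result clearly shows the IDE cohort alone

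*Combined protocol and SAP*

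**What the plan says.** Section 5.1 gives the purpose as showing safety and effectiveness in patients "undergoing one level spinal fusion, in combination with interbody fusion device". Section 5.2 gives every IDE patient a cleared PEEK cage by PLIF or TLIF.

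Sections 5.5 and 5.13.1 analyse about 100 patients: the 55 IDE patients plus about 45 from the ongoing OUS study. Section 5.13.1 discloses the surgical difference: "The IDE study includes the use of an interbody fusion device while the OUS study does not". It argues that the OUS data "may be regarded as worst case in terms of fusion rates as only posterolateral fusion was made and interbody fusion device was not used". It also cites the same system, a similar population once non-DDD patients are left out, similar visit times and the same assessment tools for fusion, safety, pain, function and well-being. It reports that FDA found the sample size sufficient.

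Section 5.13.2 compares baseline and prognostic characteristics before pooling, explicitly including IDE against ongoing-OUS patients. If the data are dissimilar, pooling may be reconsidered. Primary results are also to be shown by US and OUS sites. The section then closes by treating pooling with the ongoing OUS study as already acceptable, referring back to 5.13.1.

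On enrolment, section 5.2 says: "At least 30 patients will be enrolled at US sites with the rest being enrolled in sites outside the US". Section 5.12 states precision for 100 patients and sets a 41% overall success value without naming the analysis set. Section 5.2 says that "the statistical analyses of the suggested study will be descriptive in nature".

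**The concern.** Nearly half of the analysed patients did not have the procedure named in the purpose. The composite needs fusion, pain, function and safety success in the same patient. An argument that leaving out the cage is conservative for fusion does not say which way pain, function, neurological status, device-related serious events or reinterventions would move.

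If the 41% value is read on the pooled set, the pooled rate can sit above or below the rate in the IDE cohort. The protection in a descriptive analysis is to show the two cohorts side by side. The split that is named, by site location, does not do this cleanly, because OUS sites also enrol IDE patients. The plan also sets up a comparison to decide on pooling and then appears to settle the matter in advance for the cohort where it matters most.

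**Working it through.** **1. The plan's own precision.** Inputs from section 5.12: fusion 88%, safety events 13.5%, n = 100. Half-width = 1.96 × √(p(1−p)/n).

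- Fusion: 1.96 × √(0.88 × 0.12/100) = 6.37 points (plan: 6.4).
- Safety: 1.96 × √(0.135 × 0.865/100) = 6.70 points (plan: 6.7).

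Both figures reproduce. The same formula at n = 55 gives 8.59 and 9.03 points.

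**2. What the site split shows.** Inputs: 55 IDE patients, at least 30 in the US, about 45 ongoing-OUS patients.

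- US stratum: at least 30 patients, all with a cage.
- OUS stratum: at most 55 − 30 = 25 with a cage, plus about 45 without. The cage share is at most 25/70 = 36%.

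The US stratum is a clean view of at least 30 of the 55. Up to 25 IDE patients appear only in the mixed stratum.

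**3. Does the literature control support the directional argument?** I split the arms of Tables 2, 4 and 6 by procedure. ODI and VAS means are weighted by the number of patients.

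| Outcome | Interbody arms | Posterolateral-only arms |
|---|---|---|
| Fusion | (58+67+21+19+82+46+47)/383 = 340/383 = 88.8% | (54+19+29+15+31)/173 = 148/173 = 85.5% |
| ODI improvement | (65×8.8 + 71×22.9 + 30×21.4 + 61×26.1)/227 = 19.5 | (59×14.8 + 35×15.6)/94 = 15.1 |
| VAS improvement | (65×19.9 + 71×32 + 30×35 + 61×36.3)/227 = 30.1 | (59×22.9 + 35×22.7)/94 = 22.8 |

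Together the arms give 488/556 for fusion, as in Table 3, and 18.23 and 27.96 for ODI and VAS (plan: 18.22 and 27.96).

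For fusion the direction agrees with the plan. For pain and function it is not consistent. In the one randomised study with both kinds of arm in Tables 4 and 6, improvement was larger without interbody fusion: ODI 14.8 against 8.8, VAS 22.9 against 19.9. Across all arms the order reverses. The plan justifies pooling these outcomes because "similar values were reported for one- and 2-level and for one- and two years"; it does not discuss procedure.

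**4. Can the pooled 41% differ from the IDE rate?** Pooled rate = 0.55 × IDE + 0.45 × OUS. An OUS rate of 51% with an IDE rate of 32.8% pools to 41%; so does 31% with 49.2%.

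The documents give no composite rate for either cohort, so the following chances are illustrations under assumed true rates. I read the rule as at least 41 of 100 pooled, or at least 23 of 55 in the IDE cohort (23/55 = 41.8%, slightly stricter).

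| Assumed IDE / OUS | Pooled meets rule | IDE alone meets rule |
|---|---|---|
| 35% / 50% | 60% | 18% |
| 35% / 40% | 25% | 18% |
| 35% / 35% | 12.5% | 18% |
| 45% / 40% | 67% | 73% |
| 45% / 30% | 32% | 73% |

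The discrepancy can run either way. It is large only when the assumed gap between cohorts is large.

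**The case against.** The pooling is disclosed, FDA agreement on sample size is reported, and the analyses are descriptive. The fusion benchmark itself contains posterolateral-only arms, since study selection required that "the intervention included instrumented fusion (interbody and/or posterolateral fusion), in at least one arm of the study". All of this stands, and the point does not ask for the pooling to be undone.

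Section 5.13.1 gives more than the fusion argument: same device, similar population, same tools for pain, function and safety. That also stands. It supports comparable measurement, but it does not say how leaving out the cage would affect those outcomes.

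Section 5.13.2 uses its US and OUS labels loosely enough to cover IDE against ongoing-OUS patients, so the promised stratified result could be read that way; section 5.13.4 also allows subgroup summaries where necessary. This is the best answer. But the sentence on stratified results refers to sites, and 5.13.1 stresses that OUS sites enrol IDE patients. If a by-study split was meant, one sentence settles it.

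The closing sentence on the OUS study need not override the comparison and the re-evaluation clause. It does leave unclear which governs.

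The literature splits are weak evidence: they cross studies with different baselines, and the largest improvements come from anterior interbody cohorts, one of them entirely two-level. I use them only to show that the documents establish no direction for pain and function.

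Three stronger readings are tempting. A reader might infer that nothing would reveal a difference between the procedures; the cage-only US stratum contradicts that. A reader might infer that OUS patients cannot meet inclusion criterion 2; the criterion speaks of being a candidate for the procedure, and 5.13.1 explains what eligibility means for them. A reader might infer that pooling biases the result in the sponsor's favour; no figures in the documents show that.

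**Conclusion.** The point holds as a gap in planned reporting. The directional argument for pooling covers fusion only, while pain, function and safety also decide the composite. The one stratified primary result that is named isolates at least 30 of the 55 IDE patients and can leave up to 25 mixed with about 45 who had a different procedure. The handling of the ongoing OUS study in 5.13.2 needs to be reconciled with its own comparison.

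The firm numbers are the stratum counts and the precision: ±8.6 and ±9.0 points for the 55, against the stated ±6.4 and ±6.7 for 100. They rest on the plan's assumed rates, on about 45 OUS patients qualifying and, for the 25, on US enrolment at its minimum. The chances of meeting 41% are illustrations and depend strongly on the assumed gap. That the 41% rule applies to the pooled set is an inference from 5.13.1 and the ITT definition in 5.13.3.

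**What to change.** - In 5.13.2, add primary results (composite, fusion, safety, pain, function) by study, IDE (n = 55) against ongoing OUS study (about 45), beside the pooled result.
- In 5.13.2, reword the closing sentence on the ongoing OUS study so that the planned baseline comparison and the re-evaluation clause govern pooling.
- In 5.12, if the 41% rule is meant for the pooled set, say so, and show the IDE-only rate beside it.
- In 5.12, add the n = 55 half-widths for the two rates already covered: fusion ±8.6 and safety ±9.0 points.

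The pooled set may stay primary. The cost is one descriptive table and some wording, with no new patients or visits. The stated precision for the IDE cohort will look less favourable, and pooling with the OUS study will depend on the comparison instead of being settled beforehand.

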5.10 EVALUATION OF PRIMARY OUTCOME MEASURES

5.10.1 FUSION EVALUATION

Fusion will be evaluated radiographically, by A-P, lateral and flexion/extension X-Rays (flexion/extension films will be used for the assessment of angular and translational motions). As detailed below, in case of inconclusive findings regarding bridging bone, a CT scan will also be performed, and evaluated by the core lab.

Fusion assessment shall be made postoperatively, starting at 6 months and at each follow-up session afterwards.

Each fusion area (between the endplates, at right posterolateral, and at left posterolateral, as applicable) will be assessed separately.

All radiographs will be read by two independent, board-certified, radiologists from Medical Metrics, Inc., with experience in musculoskeletal imaging, blinded to clinical outcomes, and without any financial interest in CarboFix Orthopedics, to ensure consistent reading of the radiographs and elimination of bias. In the case of a disagreement between the two radiographic assessors, a third independent reviewer will evaluate the radiographic images to adjudicate the findings.

Please refer to **Appendix D** for radiographic protocols, including Image Acquisition Protocol, Image Transfer Protocol, and Radiographic Evaluation Protocol. All said protocols were provided to CarboFix by Medical Metrics, Inc.

Fusion Radiographic Patient Success is defined when all the following radiographic endpoints are met at 24 months:

- a. Angular motion < 3°; AND
- b. Translational motion < 3 mm; AND
- c. Presence of continuous bridging bone between the involved motion segment, *i.e.*:
 - Presence of interbody (between endplates) bridging bone and absence of radiolucency > 50%; OR
 - Presence of left posterolateral bridging bone; OR
 - Presence of left posterolateral bridging bone.

Regarding angular motion, reporting of subjects will be provided in the following three groups:

- 1. those with $\leq 3^{\circ}$ total angular motion,
- 2. those between 3° and 5° of motion, and
- 3. those with $\geq 5^{\circ}$ of motion.

In case bone graft would be placed in the interbody space as well as posterolaterally, on both sides, bridging would be assessed in each of the three areas. Bridging in any one area would be considered adequate to document the presence of affirmative bridging.

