- f. Providing a clear Instructions for Use document (IFU) and Surgical Technique. Among other things, these documents include description of the system and its components (including figures), indications for use and contraindications, possible adverse events, warnings and precautions, instructions regarding system preparation, surgical procedure description, information regarding the compatibility of the product with other devices, and information regarding product packaging and sterilization.
- g. Conducting additional validations and verifications, as applicable, such as sterilization validation.

The following paragraphs specifically address the risks indicated above, and the measures by which those potential risks are minimized.

A. Risks Associated with Undergoing Surgery

General operative-related complications (such as infection/sepsis, bleeding/vascular injury, respiratory and cardiac complications, anesthesia, wound complications and

pain, *etc.*, as listed above) are expected to be similar in nature and not in higher rates compared to those seen with other pedicle screw systems, as the surgical procedure is the same.

As the implantation procedure is similar to that used for other pedicle screw system implantation, using similar surgical instruments, and as cleared interbody fusion device is used, no additional/special hazards are expected to rise from the operation procedure itself.

It is noted, that the implantation procedure and the performance of the surgical instruments were also evaluated during cadaveric study.

In addition, the CarboClear System is currently under multi-center study conducted out-of-the-US. So far, 47 patients were already treated with the system, with a follow-up duration of up to over one year (40 of which had diagnosis that complies with the indications proposed in the IDE (*i.e.*, DDD patients with up to Grade I spondylolisthesis). The following adverse event, which may be categorized as related to undergoing surgery, was reported in the said study:

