Regarding the risk of infection due to non-sterile device - the implants will be supplied sterile (by moist-heat steam) and labeled for single use. The multi-use surgical instruments will be supplied non-sterile, to be steam sterilized by the user. The steam sterilizations for the system components were validated to assure SAL of 10^{-6} , and bioburden tests are conducted periodically.

Information regarding the sterilization of the implants and the cleaning and sterilization of the reusable surgical instruments is provided in the Investigator Brochure.

Regarding the ongoing OUS study - it is emphasized, that no device-related adverse events or device malfunctions were reported in any of the 47 patients implanted with the system. No failure was observed to any of the components implanted (about 180 pedicle screws (and locking elements), with about 90 rods for all 47 patients operated).

In addition, as indicated earlier, fusion - determined by X-Ray images indicating continuous fusion in between transverse processes and/or facet joints (AP and lateral X-Rays) – was indicated in the following rates (for the 40 DDD patients; please note

that for part of the patients, evaluation of translational and angular motion using flexion/extension radiographs was also conducted):

- At 6 months (1 level): 25/26 patients (96.2%);
- At 12 months (1 level): 3/3 patients (100%);
- At 6 months (2 levels): 1/1 (100%).

The on-going clinical investigation with the CarboClear device also supports the proper visualization of implant components, either during operation or at follow-up period. Also, no allergic reaction to the implant was reported.

As it is postulated, based on all the above, that the risk of device breakage/loosening/disassembly/migration; non/delayed fusion; or foreign body reaction to the device, would not be at a higher rate than seen for other cleared, rigid, pedicle screw systems, it is expected that the risk of re-operation due to these risks will be at similar rate as the rate reported for other pedicle screw systems.

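### About 45 of the 100 pooled patients come from a study whose interim fusion calls did not always include the motion test, and the plan does not prevent their being scored fused without it

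*Combined protocol and SAP*

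**What the plan says.** Section 5.13.1 sets the analysis set. "Fifty five (55) patients will participate in the IDE study", and "the statistical analysis will be conducted for a total sample size of 100 patients". The difference comes from the ongoing OUS study: "Only currently enrolled patients in the ongoing OUS sites that are adequately per IDE protocol (about 45 patients) will be considered in the statistical analysis". Whether a patient is adequate is to be judged mainly on the IDE eligibility criteria. The section supports the pooling with this statement: "The endpoints for the IDE study are also evaluated in the ongoing OUS study, using the same assessment tools: fusion (radiographs").

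Section 5.10.1 defines IDE fusion at 24 months as angular motion below 3°, translation below 3 mm and continuous bridging bone, all three together. It states that "flexion/extension films will be used for the assessment of angular and translational motions". Section 5.12 repeats both motion limits among the criteria that must all be met for overall success.

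The ongoing-OUS paragraphs that close part D of section 5.14.2 (Risk Reduction Measures) describe how fusion had been called so far in that study: "determined by X-Ray images indicating continuous fusion in between transverse processes and/or facet joints (AP and lateral X-Rays"). They add that "for part of the patients, evaluation of translational and angular motion using flexion/extension radiographs was also conducted". The rates given are 25/26 (96.2%) at 6 months and 3/3 at 12 months for one level, and 1/1 at 6 months for two levels.

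**The concern.** The pooling argument depends on fusion being measured in the same way in both studies. The plan's own account of the OUS study describes a bridging call with motion checked in an unstated share of patients. A bridged patient with 3° or more of motion is not fused under section 5.10.1, but could be fused under the OUS call.

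The plan treats this as a difference that matters. Section 5.2.1.A classes literature studies without flexion/extension films as less rigorous, and says that less stringent definitions yield higher fusion rates. In the literature control, a looser definition raises the bar for the device. In the device's own data it lowers it.

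Fusion is reported against an expected 88%, and it is one component of the composite on which the 41% study success criterion rests. The section 5.13.1 argument that OUS data are a worst case concerns the absence of an interbody device. It does not address how fusion was measured.

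**Working it through.** **Inputs from the documents.** IDE patients 55; OUS patients about 45; pooled total 100 (section 5.13.1). Expected fusion 88% with a half-width of ±6.4% (section 5.12). At the time of writing, 47 OUS patients had been treated, "40 of which had diagnosis that complies with the indications proposed in the IDE" (section 5.14.2).

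**Share of the analysis set.** 45/(55 + 45) = 45%. If only the 40 with a compliant diagnosis entered, the share would be 40/(55 + 40) = 42%.

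**The plan's own figure.** Half-width = 1.96 × √(0.88 × 0.12/100) = 6.37 points, with lower bound 88 − 6.4 = 81.6%. Both match section 5.12.

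**Does any text close the gap?**
- Admission (5.13.1): mainly eligibility. Motion films are not named as a condition.
- Common radiographic protocol and readers (5.13.2): the argument rests on all sites following this protocol, and the section opens with the up to eight sites of this study. Extension to the ongoing OUS study is not stated.
- Poolability checks (5.13.2): baseline characteristics and cage type, not endpoint ascertainment. For the ongoing OUS study the section refers back to 5.13.1.
- Stratification by US and OUS sites (5.13.2): this does not isolate the 45. At least 30 of the 55 IDE patients are to be from the US, so up to 55 − 30 = 25 IDE patients could fall in the OUS stratum.
- Missing data (5.8 and 5.13.4): interpolation and last value carried forward are allowed. A patient with missing data may be regarded as a success on earlier information, for instance where fusion preceded withdrawal and no adverse event was seen.

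None of these says how an OUS patient without 24-month motion films is scored.

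**Size if such patients are scored on bridging alone.** The documents give none of the three inputs below, so all are assumptions: share of the 45 without motion films, 25% to 100%; share of those bridged, 90%; share of bridged patients failing a motion limit, 5% to 15%.

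Excess fused per 100 = 45 × share without films × 0.90 × share failing motion
- Low: 45 × 0.25 × 0.90 × 0.05 = 0.5
- High: 45 × 1.00 × 0.90 × 0.15 = 6.1

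This is a scenario range, not a bound. For example, if 75% lack films and 20% of all those patients are wrongly called fused, the result is 45 × 0.75 × 0.20 = 6.8.

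**Effect on the composite.** A wrongly fused patient changes overall success only if pain, function and safety also pass. Taking the section 5.12 values and assuming independence: 0.73 × 0.55 × (1 − 0.135) = 0.347. Then 0.5 × 0.347 ≈ 0.2 and 6.1 × 0.347 ≈ 2.1 points. If the components are correlated so that overall success is the 41% target, the factor is 0.41/0.88 = 0.466 and the upper figure is 6.1 × 0.466 ≈ 2.8 points.

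**Size if the motion requirement is enforced.** With m the share of OUS patients without films, evaluable n = 55 + 45(1 − m). The last column scores those without films as not fused, with 88% fused among the rest.

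| m | Evaluable n | Half-width at 88% | Pooled rate, no films = not fused |
|---|---|---|---|
| 25% | 88.75 | ±6.8 | 78.1% |
| 50% | 77.5 | ±7.2 | 68.2% |
| 75% | 66.25 | ±7.8 | 58.3% |
| 100% (IDE only) | 55 | ±8.6 (lower bound 79.4%) | 48.4% |

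**The case against.** The strongest reply is that the OUS text in section 5.14.2 is an interim report at 6 and 12 months, placed in a risk section, and not a scoring rule. Follow-up then reached little more than a year, so it says nothing about imaging at 24 months. Section 5.12 requires every criterion, and read literally it would not count a patient without motion films as a success. Section 5.13.1 also limits OUS patients to those adequate under the IDE protocol, with eligibility the main test but not the only one. The Investigator Brochure and radiographic appendix, which may settle the matter, are not available here.

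Much of this stands. A reader might infer that OUS patients will be scored on bridging alone, or that the pooled fusion rate is already known to be inflated. The documents support neither: they do not describe the 24-month OUS films, and they set no looser rule for these patients.

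The reply does not close the gap. The plan gives no scoring rule for a patient without motion films, and the discretion in section 5.13.4 points towards success. If the literal reading governs, the claim of 100 effective patients is unsupported for fusion.

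Two further points are fair. Several literature studies also lacked motion assessment, so the bias relative to the 88% comparator is smaller than the bias against the IDE definition. And simply excluding patients without films would be a complete-case rule, at odds with the ITT primary analysis in section 5.13.3.

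**Conclusion.** The concern holds as an unclosed gap. The statement in section 5.13.1 that fusion is assessed alike is not supported by the plan's own description of the OUS study. For about 45% of the analysis set, nothing guarantees measurement of a required part of the primary endpoint.

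Following the plan as written can give either of two results. Pooled fusion may be biased upward, by about 0.5 to 6 points under the assumed film, bridging and motion shares, with a smaller effect on the composite (about 0.2 to 2 points under independence). Or, under the literal definition, fewer than 100 patients can be evaluated for fusion. The upper end of the first range is about as large as the plan's ±6.4-point half-width. The true size cannot be computed, because the documents give neither the number of OUS patients with motion films nor the share of bridged patients with excess motion. That the bias will in fact occur is not shown.

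**What to change.** Amend section 5.13.1, with matching text in sections 5.8 and 5.13.4:

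1. Remove the claim of identical assessment tools as it applies to fusion.
2. Require that 24-month films of ongoing-OUS patients be read by the same core lab to the section 5.10.1 definition.
3. State that no OUS patient may be scored fused, or an overall success, on bridging alone or under the section 5.13.4 discretion when motion films are absent. Interpolation and carrying forward should not supply the motion result either.
4. Report how many OUS patients have 24-month motion films.
5. Report fusion and overall success for the 55 IDE patients alone, beside the pooled result.
6. Keep OUS patients without films in the ITT set for pain, function and safety. Treat their fusion and overall success as missing in the pooled analysis, and as not fused in a sensitivity analysis. The latter is an extreme bound and should be labelled so.

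The cost is protocol wording, core-lab reading of existing films, and a wider fusion interval: from ±6.4 to about ±6.8 if 25% lack films, ±7.2 if 50% do, and ±8.6 for the IDE patients alone. At the time of writing, OUS follow-up had reached only a little over one year, so the rule could be set before 24-month results are known.
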